### **3.2.1 Pharmacokinetics Assessment**

Within 2 weeks after screening, subjects will receive a single infusion of 70 mg/kg *Octafibrin*. Before the start of the PK phase, there must be an at least 2-week wash-out period of any fibrinogen containing product.

Before first injection vital signs and blood draws for baseline fibrinogen levels will be assessed. Retention serum samples for potential retesting will be collected within 30 minutes before the PK infusion. At 1 and 3 hours post-infusion, vital signs and fibrinogen for PK will be assessed. Subjects will be further followed on days 2, 4, 7, 10, and 14 and undergo study assessments as specified.

All adverse events (AEs), including thromboembolic events and early signs of allergic or hypersensitivity reactions, occurring between the start of the first *Octafibrin* infusion and the end of the PK phase will be recorded.

All SAEs occurring after the first IMP infusion will be documented and reported for a patient throughout the duration of the patient's participation in the study or as required to meet local regulations.

At the end of the study (i.e., when at least 12 patients have completed the PK assessment, 3 patients in each of the specified age groups have had at least one treated bleeding episode, and a minimum of 2 surgical procedures have been performed), all patients having received any IMP will be asked to return for a Study Completion Visit.

### 3.2.2 On-demand Treatment of Acute Bleeding

Subjects presenting to the study site for on-demand treatment of an acute bleeding episode who are eligible for enrolment and whose legal guardians have provided written informed consent will be included into the study.

Each subject will receive at least 1 infusion of *Octafibrin* for the treatment of acute bleeding on Day 1. The individual **subject observation and follow-up period** for each documented episode starts with the first dose of *Octafibrin* administered for on-demand treatment of an acute bleeding episode (Day 1) and will be followed up to at least Day 30.

Each subject's **treatment observation period** is defined according to the severity of the event and will last at least 3 days for minor and 7 days for major bleeding episodes.

On each day of the treatment observation period (i.e., 3 days for minor and 7 days for major bleeding), fibrinogen plasma levels will be measured daily to determine whether additional infusions of *Octafibrin* are needed:

- Additional infusions of *Octafibrin* **should** be administered if the actual fibrinogen plasma level measured on these days is below the accepted lower limit of the target level (80 mg/dL for minor bleeding, 130 mg/dL for major bleeding).
- If the actual fibrinogen plasma level is above the accepted lower limit of the target level, *Octafibrin* **should not** be administered.

The actual treatment duration will be determined by the investigator based on his/her judgement of the subject's condition.

All adverse events (AEs), including thromboembolic events and early signs of allergic or hypersensitivity reactions, occurring between the start of the first *Octafibrin* infusion and the end of each 30-day observation and follow-up period will be recorded. The detection of thromboembolic events (TEEs) will be supported by completing a TEE questionnaire at each study visit for the treatment of bleeding episodes and for surgeries. Concomitant medications will also be recorded throughout each 30-day observation and follow-up period.

All SAEs occurring after the first IMP infusion will be documented and reported for a patient throughout the duration of the patient's participation in the study or as required to meet local regulations. Also, any concomitant medications used to treat an SAE will be recorded.

At the end of the study (i.e., when at least 3 patients in each of the specified age groups have had at least one treated bleeding episode and when a minimum of 2 surgical procedures have been performed) all patients having received any IMP will be asked to return for a Study Completion Visit.

### 3.2.3 Surgical Prophylaxis

Subjects planning to undergo elective surgery may also be enrolled in the study.

Within 3 hours prior to surgery, each patient will receive a loading infusion of *Octafibrin* to achieve a recommended fibrinogen plasma level of 100 mg/dL for minor surgeries and 150 mg/dL for major surgeries.

Each subject's **surgical observation period** starts with the first dose of *Octafibrin* administered prior to elective surgery (Day 1) and, depending on the severity of the event, will last at least 3 post-operative days for minor and 7 post-operative days for major surgeries or until the day of the last post-operative infusion, whichever comes last.

On each post-operative day, fibrinogen plasma levels will be measured daily (i.e., at least 3 post-operative days for minor and 7 post-operative days for major surgeries) to determine whether additional infusions of *Octafibrin* are needed.

- Additional infusions of *Octafibrin* **should** be administered if the actual fibrinogen plasma level measured on subsequent days is below the accepted lower limit of the target level (80 mg/dL for minor surgeries, 130 mg/dL for major surgery).
- If the fibrinogen plasma level is greater than or equal to the accepted lower limit of the target fibrinogen plasma level, *Octafibrin* **should not** be administered.

The actual treatment duration will be determined by the investigator based on his/her judgement of the subject's condition.

All AEs, including thromboembolic events and early signs of allergic or hypersensitivity reactions, occurring between first infusion of IMP before the start of surgery and the Last Post-Operative Day will be recorded. The detection of thromboembolic events (TEEs) will be supported by completing a TEE questionnaire at each study visit for the treatment of bleeding episodes and for surgeries.

All SAEs occurring after the first IMP infusion will be documented and reported for a patient throughout the duration of the patient's participation in the study or as required to meet local regulations. Also, any concomitant medications used to treat an SAE will be recorded.

At the end of the study (i.e., when at least 3 patients in each of the specified age groups have had at least one treated bleeding episode and when a minimum of 2 surgical procedures have been performed. All patients having received any IMP will be asked to return for a Study Completion Visit.

### 3.3 Discussion of Study Design and Choice of Control Group(s)

As there are currently no guidelines concerning fibrinogen concentrates in either the US or the EU, the study was designed following established programs for Factor IX concentrates.

Typically, the clinical evaluation of a new concentrate initially examines the IVR and the PK properties of the principal active factor. Prior to initiating the present study, comparative PK data in adults were obtained in study FORMA-01. A study similar to the one described in this protocol, i.e., FORMA-04, is currently ongoing in adults patients (FORMA-02), the main difference being the additional examination of PK properties in paediatric patients in FORMA-04.

The open-label uncontrolled design and choice of study objectives are motivated by regulatory requirements for Factor IX [14] and discussions with the regulatory bodies.

The median response value used in the fibrinogen dosage calculation is the median incremental *in vivo* recovery reported in the final analysis of study FORMA-01.

Although all bleeding episodes occurring throughout the study observation period will be documented, only the first bleeding episode per patient will be used for the analysis of the primary endpoint (see Section 3.1.1). This is because the study will end once at least 12 patients have undergone PK assessment and the 6th patient (i.e., at least 3 patients in each of the specified age groups) has at least one documented bleeding episode, potentially resulting in a large diversity in the number of bleeding episodes between patients; also, the haemostatic outcomes in different bleeding episodes within one patient cannot be regarded as independent/uncorrelated. The entirety of bleeding episodes documented in the study will be assessed as a secondary endpoint (see Section 3.1.2).

## 4 STUDY POPULATION

### 4.1 Population Base

At least 12 paediatric subjects with clinically diagnosed congenital fibrinogen deficiency (i.e., afibrinogenaemia or severe hypofibrinogenaemia) will be enrolled into the study and undergo PK assessment. Of these 12 subjects, at least 6 subjects will undergo on-demand treatment of 6 first bleeding episodes. Of these 6 subjects, at least 3 should be aged between 0 and <6 years and 3 should be aged between 6 and <12 years.

### 4.2 Inclusion Criteria

Subjects who meet all of the following criteria are eligible for the study:

1. Aged <12 years (at the start of treatment)
2. Documented diagnosis of congenital fibrinogen deficiency, expected to require on-demand treatment for bleeding or surgical prophylaxis:
  - Fibrinogen deficiency manifested as afibrinogenaemia or severe hypofibrinogenaemia
  - Historical plasma fibrinogen activity of <50 mg/dL or levels below the limit of detection of the local assay method
3. Expected to have an acute bleeding episode (spontaneous or after trauma) or planning to undergo elective surgery.
4. Informed consent signed by the subject's legal guardian

### 4.3 Exclusion Criteria

Subjects who meet any of the following criteria are not eligible for the study:

1. Life expectancy <6 months
2. Bleeding disorder other than congenital fibrinogen deficiency, including dysfibrinogenaemia
3. Prophylactic treatment with a fibrinogen concentrate
4. Treatment with:
  - Any fibrinogen concentrate or other fibrinogen-containing blood product within 2 weeks prior to start of treatment for the PK phase, a bleeding episode, or surgery
  - Any coagulation-active drug (i.e., non-steroidal anti-inflammatory drugs, warfarin, coumarin derivatives, platelet aggregation inhibitors) within 1 week prior to start of the PK phase or treatment for the bleeding episode or surgery, or as a planned or expected medication during the time period from Day 1 until 24 hours (i.e., 1 day) after the last *Octafibrin* infusion

5. Presence or history of:
  - Hypersensitivity to study medication
  - Deep vein thrombosis or pulmonary embolism within 1 year prior to start of treatment for the bleeding episode or surgery
  - Arterial thrombosis within 1 year prior to start of treatment for the bleeding episode or surgery
  - Hypersensitivity to human plasma proteins
  - Oesophageal varicose bleeding
  - End-stage liver disease (i.e., Child-Pugh score B or C)
6. Known positive HIV infection with a viral load  $>200$  particles/ $\mu$ L or  $>400,000$  copies/mL
7. Polytrauma 1 year prior to start of treatment for the bleeding episode or surgery
8. Diagnosis or suspicion of a neutralising anti-fibrinogen inhibitor currently or at any time in the past
9. Acute or chronic medical condition which may, in the opinion of investigator, affect the conduct of the study, including subjects receiving immune-modulating drugs (other than anti-retroviral chemotherapy), such as alpha-interferon, prednisone (equivalent to  $>10$  mg/day), or similar drugs, at study start
10. Treatment with IMP in another interventional clinical study currently or during the past 4 weeks

**NOTE:** If the period between screening and treatment or between treatments is more than 3 months, informed consent will be re-reviewed and confirmed prior to treatment, and details of the review process will be recorded in the patient chart and indicated in the CRF by the investigator. Also, inclusion/exclusion criteria will be confirmed prior to treatment.

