### 2. Thromboembolic events

Such events have been reported in patients treated with plasma-derived fibrinogen concentrates. Thus, patients receiving *Octafibrin* should be monitored for signs and symptoms of thrombosis.

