#### **4.4.2 Forbidden Concomitant Therapy**

Subjects may not receive any coagulation-active drug (i.e., non-steroidal anti-inflammatory drugs, warfarin, coumarin derivatives, platelet aggregation inhibitors) within 1 week prior to start of treatment for the bleeding episode or surgery, or as a planned or expected medication during the time period from Day 1 until 24 hours after the last *Octafibrin* infusion.

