### 6.2.2 Planned Duration for an Individual Subject

All patients will undergo a PK study after screening. This will have a duration of 14 days, after which a patient can be treated for a bleeding episode or planned surgical procedure when they occur.

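### The one-year thrombosis and polytrauma exclusions are timed to a bleed or surgery, not to the PK infusion every child receives first, so they cannot be fully applied at that exposure

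*Protocol*

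**What the plan says.** Protocol Section 4.3 contains three exclusions with a one-year look-back. Criterion 5 has two of them: "Deep vein thrombosis or pulmonary embolism within 1 year prior to start of treatment for the bleeding episode or surgery" and "Arterial thrombosis within 1 year prior to start of treatment for the bleeding episode or surgery". Criterion 7 is the third: "Polytrauma 1 year prior to start of treatment for the bleeding episode or surgery". The synopsis lists them in the same terms.

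Criterion 4, in the same list, is anchored differently. Prior fibrinogen products are barred "within 2 weeks prior to start of treatment for the PK phase, a bleeding episode, or surgery", and coagulation-active drugs "within 1 week prior to start of the PK phase or treatment for the bleeding episode or surgery". Section 4.4.2 repeats the ban on coagulation-active drugs but times it "within 1 week prior to start of treatment for the bleeding episode or surgery", without the PK phase.

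On sequence, Section 6.2.2 states: "All patients will undergo a PK study after screening". Bleeds and surgeries are treated after that 14-day phase. Section 3.2.1 places the single 70 mg/kg infusion within two weeks of screening.

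On risk, Section 1.5 says of thromboembolism: "Such events have been reported in patients treated with plasma-derived fibrinogen concentrates". Section 2.2 includes thromboembolic complications in the safety objective.

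**The concern.** A time-limited exclusion works only if its reference date is known when the decision to expose the child is taken. Here the first planned exposure is the PK infusion, and the three one-year windows count back from a later event that may have no date or may never happen.

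Take a child with a deep vein thrombosis three months before screening who is enrolled because a bleed is expected. The site has no bleed date to count from. One site may infuse and another may defer, and both could say they followed the text. At stake are consistent application of a safety exclusion across sites, and a clear statement of which thrombotic history the safety population was meant to leave out.

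**Working it through.** The plan gives no figure to reproduce on this point. The check compares wording, with supporting arithmetic.

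**Step 1. Anchors side by side.**

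| Rule | Look-back | PK phase named | Bleed or surgery named |
|---|---|---|---|
| 4.3 criterion 4, fibrinogen products | 2 weeks | yes | yes |
| 4.3 criterion 4, coagulation-active drugs | 1 week | yes | yes |
| 4.3 criterion 5, venous thrombosis or embolism | 1 year | no | yes |
| 4.3 criterion 5, arterial thrombosis | 1 year | no | yes |
| 4.3 criterion 7, polytrauma | 1 year | no | yes |
| 4.4.2, coagulation-active drugs | 1 week | no | yes |

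**Step 2. Can the shorter anchor be read as including PK?** No. The second limb of criterion 4, "within 1 week prior to start of the PK phase or treatment for the bleeding episode or surgery", sets the PK phase beside treatment for a bleed or surgery as an alternative. The second phrase therefore does not contain the first.

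**Step 3. What a site can conclude at screening.** Consider a child with a qualifying event in the past year:

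- Surgery already dated within one year of the event: the criterion is met. The child is excluded from the study as a whole, PK included, so there is no gap.
- Surgery dated more than one year after the event: the criterion is not met, although the PK infusion may fall inside the year. The infusion is not covered.
- Awaiting a bleed, which inclusion criterion 3 allows: there is no date to count from, so the criterion cannot be evaluated.
- No later bleed or surgery: the window never gains a reference date. At screening this child looks the same as the one before.

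**Step 4. How much of the year before PK is missed.** If the bleed or surgery falls t days after the PK infusion, a window of 365 days before it leaves min(t, 365) days of the pre-PK year uncovered.

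| t (days) | Uncovered days | Share of the year |
|---|---|---|
| 14 | 14 | 3.8% |
| 90 | 90 | 24.7% |
| 180 | 180 | 49.3% |
| 365 or more, or no event | 365 | 100% |

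For an undated bleed, even the covered part becomes known only after the infusion has been given.

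**Step 5. Size of the PK exposure.** The inputs are 70 mg/kg (Section 5.4.1), the median response 1.77 (Section 5.4.2), and targets of 100 and 150 mg/dL (Section 5.4.3). The unit, mg/dL per mg/kg, is taken from SAP Section 3. It fits the dose formula; the Section 5.4.2 footnote prints g/L, which does not.

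- Expected rise: 70 x 1.77 = 123.9 mg/dL.
- Calculated doses from a zero baseline: 100 / 1.77 = 56.5 mg/kg (minor) and 150 / 1.77 = 84.7 mg/kg (major).

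The PK dose lies between the two calculated first doses.

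**Step 6. Children who may have PK only.** The minimums are 12 with PK and 6 with a treated bleed (Section 4.1). At those minimums, 12 - 6 = 6 children (50%) could have no treated bleed. Unless they have surgery, the windows never apply to them. Section 4.5.2 foresees children who receive PK only.

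**The case against.** The strongest reply is that the gap is narrower than it looks and partly covered elsewhere.

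- *Eligibility is for the whole study.* This stands for surgery already dated within a year of the event. A reader might infer that any child with a recent thrombosis is eligible for the PK dose as written. The text does not say so: for an undated bleed the criterion is indeterminate, which is not the same as satisfied.
- *Criterion 9 lets the investigator exclude on medical grounds.* True, but it is discretionary and names neither thrombosis nor polytrauma.
- *Criterion 4 catches a child on warfarin, coumarins or platelet inhibitors within a week of PK.* True, but not one who has stopped or who takes another agent.
- *Criteria are confirmed again before treatment after more than three months.* The PK infusion comes within two weeks of screening, so this would not normally be triggered, and it re-applies the same wording.
- *Thromboembolic events are recorded throughout the PK phase.* That detects events after exposure; it does not select children before it.
- *A similar peak is not a similar thrombotic exposure.* Fair. Treatment may involve repeated infusions, so the 123.9 mg/dL figure places the single infusion among calculated first doses and shows no more than that.
- *The documents link polytrauma to no PK risk.* Also fair. For criterion 7 the point is consistency of the anchor.

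Some wording also cuts against PK first: Section 6.1.4.1 calls the surgery-day dose the first, and Section 3.2.2 speaks of including subjects who present with a bleed. These conflict with Section 6.2.2 and supply no PK anchor.

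**Conclusion.** The point holds in this form: as written, the one-year thrombosis and polytrauma windows are not tied to the PK infusion, the first exposure planned for every child. They cannot be evaluated there for a child awaiting a bleed, and they do not cover it where surgery is more than a year after the event or where no bleed or surgery follows. This should be corrected, but it does not undermine the planned analyses.

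The planned minimum of 12 counts children exposed to PK, not children affected. The documents do not say how many have such a history, and the number may be zero. The conclusion rests on reading Section 6.2.2 as it stands, with PK first for all, and on criterion 4's own separation of PK from treatment.

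Two stronger inferences are not supported:

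- A reader might conclude that such a child's bleeds are barred from the primary endpoint until the year has passed. The FAS and FirstBLEED definitions (Sections 9.2.2 and 9.2.5) contain no such bar, and the FirstBLEED-PP conditions (Section 9.2.6) name neither thrombosis nor polytrauma. A bleed that was treated would count.
- A reader might conclude that the PK omission in Section 4.4.2 distorts deviation classification, because SAP Section 6.2 refers to that section for confounding medication. Criterion 4 already covers the week before PK, the first item of SAP Section 6.2 makes any eligibility violation a major deviation, and the PK-PP set has its own medication criterion. What remains is an inconsistency of wording.

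**What to change.** The sponsor should reconcile the time anchors of both thrombosis lines in criterion 5 and of criterion 7 with criterion 4 and the PK-first schedule. The text should state explicitly whether and how each window applies to the PK infusion; if PK is meant to be exempt, it should say so and give the reason. Which rule applies is for the sponsor to decide. The synopsis needs the same change. For consistency, Section 4.4.2 should be aligned with criterion 4, which already names the PK phase. The passages in Sections 3.2.2 and 6.1.4.1 that read as though PK did not come first should be reconciled at the same time.

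The core edit touches seven places: three lines in Section 4.3, the same three in the synopsis, and one sentence in Section 4.4.2 (3 + 3 + 1 = 7). Doses, endpoints, analysis sets and sample size are unaffected. The cost is a small wording amendment that goes through ethics review, because Section 10.4 asks for approval of changes that could affect subject safety. Depending on the sponsor's decision, an occasional child might also be deferred from PK.

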## 4.4 Prior and Concomitant Therapy

### 4.4.1 Permitted Concomitant Therapy

Concomitant administration of therapies not interfering with the primary objective of the study is permitted. Details of any concomitant therapies, including other fibrinogen concentrates, must be recorded in the case report forms (CRFs).

Concomitant medications will be recorded only for each patient's 30-day observation and follow-up period (for on-demand treatments) and during their surgical observation period (for treatment during surgeries).

In addition, concomitant medications used to treat SAEs will be reported throughout the duration of the patient's participation in the study or as required to meet local regulations for SAE reporting.

Patients should be treated with IMP whenever possible. If, in the opinion of the investigator, a bleeding episode is not effectively stopped or surgical prophylaxis is not adequate after the recommended dose of *Octafibrin* has been administered, the subject may receive a different licensed fibrinogen concentrate (e.g., Haemocomplettan P®/RiaSTAP™) or whatever the investigator considers standard of care. The use of another licensed fibrinogen concentrate is also permitted in emergency situations, e.g., if the IMP is not available for the patient in time.

#### **4.4.2 Forbidden Concomitant Therapy**

Subjects may not receive any coagulation-active drug (i.e., non-steroidal anti-inflammatory drugs, warfarin, coumarin derivatives, platelet aggregation inhibitors) within 1 week prior to start of treatment for the bleeding episode or surgery, or as a planned or expected medication during the time period from Day 1 until 24 hours after the last *Octafibrin* infusion.

